- w All patients must receive a 5-HT₃ antagonist, ondansetron (Zofran) 8 mg PO QD or granisetron (Kytril) 1 mg PO QD prior to each dose of AZD1775. If nausea and vomiting continue, a second dose of antiemetics can be taken 8 hours later, if necessary. In addition, dexamethasone 4 mg PO will be given with each AZD1775 dose as a minimum on the first day dosing AZD1775 of every 3-5 days dosing period, unless contraindicated or not well-tolerated. Dexamethasone or the 5-HT₃ antagonist may be given by IV as needed. Please note: aprepitant [Emend] and fosaprepitant are not permitted due to known drug-drug interactions (see Section 6.7.4.2).
- x Due to frequent reports of diarrhoea with AZD1775 administration, vigorous anti-diarrhoeal treatment loperamide (Imodium) is required at the first onset of diarrhoea according to ASCO guidelines. Patients should be instructed to take oral loperamide (Imodium) 2 mg every 2 hours until diarrhoea-free for at least 12 hours.
- y When applicable, tumour markers that are elevated and are used by the Investigator to monitor for tumour response will be collected at baseline, Day 1 of each cycle, at the end of treatment and FPV. The tumour marker analysis will be performed by a local laboratory.
- z Previous individual patient genomic profile reports should be provided for this study.
- aa An optional Pharmacogenetics (PGx) sample will be obtained if the patient consents. If PGx blood sample is not collected at Cycle 1 Day 1, it can be collected any visit until the last study visit. This sample is **optional** and must be taken from patients who have provided informed consent for genetic sampling and analysis.

- bb PK samples will be collected at time of AE possibly related to AZD1775 (unless the last dose of study drug was administered > 1 week prior to the event), when imaging is performed for response assessment and at the end of treatment or progression. PK samples will no longer be required after implementation of CSP Version 5.
- cc Patients discontinuing from AZD1775 in the **absence** of PD should have CT scans performed every 3 months from the last dose of study drug until PD has been assessed by the Investigator or the patient begins a new course of cancer therapy or withdraws from the study. If PD has been assessed, patients will then be followed for survival.

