5.1 Efficacy assessments

5.1.1 Tumour assessments

RECIST v1.1 criteria will be used to assess patient response to treatment. The RECIST v1.1 guidelines for measurable, non-measurable, target lesions (TL) and non-target lesions (NTL) and the objective tumour response criteria (Complete Response [CR], Partial Response [PR], Stable Disease [SD] or progressive disease [PD]) are presented in [Appendix E](#).

The same method of assessment of tumour burden used at baseline (CT scans or magnetic resonance imaging [MRI] of the chest and abdomen/pelvis) must be used at each subsequent follow-up assessment (see [Table 2](#), [Table 3](#), and [Table 4](#)). Tumour imaging studies will be repeated every 8 weeks (± 1 week) relative to date of first dose for patients on the QD 5/9 treatment schema and every 9 weeks (± 1 week) relative to date of first dose for patients on the QD 5/2 treatment schema to assess response until objective disease progression as defined by RECIST v1.1 or withdrawal from study.

Categorisation of objective tumour response assessment will be based on the RECIST v1.1 criteria of response: CR, PR, SD and PD. Target lesion progression will be calculated in comparison to when the tumour burden was at a minimum (i.e. smallest sum of longest diameters previously recorded on study). In the absence of progression, tumour response (CR, PR, or SD) will be calculated in comparison to the baseline tumour measurements obtained before starting treatment.

If the Investigator is in doubt as to whether progression has occurred, particularly with regard to NTLs or the appearance of a new lesion, it is advisable to continue treatment until the next scheduled assessment or sooner if clinically indicated, and reassess the patient's status. If repeat scans confirm progression, then the date of the initial scan should be declared as the date of progression.

To achieve 'unequivocal progression' on the basis of non-target disease, there must be an overall level of substantial worsening in non-target disease such that, even in presence of SD or PR in target disease, the overall tumour burden has increased sufficiently to merit discontinuation of therapy. A modest 'increase' in the size of one or more NTL is usually not sufficient to qualify for unequivocal progression status.

It is important to follow the assessment schedule as closely as possible.

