8.4.5 Best objective response

The best objective response to treatment via RECIST v1.1 and Investigator assessment will be summarised by dose level cohort.

The best objective response (BOR) per subject will be derived as the best response recorded from the start of treatment until disease progression, death or subsequent cancer therapy (taking as reference for progressive disease the smallest measurements recorded since treatment started) using the Investigator reported objective response per time point. See [Appendix E](#) for how objective visit responses will be recorded.

Objective Response Rate (ORR) is the proportion of patients whose confirmed best objective response is complete response (CR) or partial response (PR). Confirmation must occur at least 4 weeks later.

Only patients with measurable disease will be included in the analysis of ORR. Patients without measureable disease at baseline will be excluded in the analysis of ORR.

The following rules will be used to determine the best objective response in each patient, assuming Assessment 1 is Baseline/Pre-treatment tumour assessment, and assessments are performed every 8 weeks on the BID and QD 5/9 Schedule or 9 weeks on either of the 5/2 Schedules.

Assessment 2	Assessment 3	Assessment 4	Best Objective Response
PD	-	-	PD
CR, PR, SD	PD	-	SD
UNK	PD	-	PD
CR, PR or SD	UNK	PD or UNK	SD
SD or UNK	CR, PR or SD	PD	SD
UNK	UNK	PD	PD

Assessment 2	Assessment 3	Assessment 4	Best Objective Response
PR	SD ⁽¹⁾	PD	SD
PR	CR or PR	PD or UNK	PR
PR	SD	PR	PR
PR	UNK	PR	PR
CR	CR	PD	CR
CR	UNK	CR	CR

(1) Only if the increase in diameter from Assessment 2 to Assessment 3 does not qualify for PD

- **Objective Response Rate (ORR)** = Proportion of patients with a confirmed best objective response of CR or PR.

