8.4.6 Progression-free survival

Progression-free survival (PFS) is defined as the time from date of first dose of AZD1775 until the date of objective disease progression or death (by any cause in the absence of progression) regardless of whether the patient withdraws from therapy or receives another anti-cancer therapy prior to progression.

The PFS will be censored in the following scenarios:

- If the patient has neither PD nor death, the PFS will be censored at last tumour assessment with CR, PR, or SD. Patient cannot be censored at “NE”.
- If patient had PD or Death occurred more than 53 days for the BID or QD 5/2 schedule or 35 days for the 5/9 schedule (2.5 tumour assessment intervals) after previous tumour assessment with CR, PR or SD, the PFS will be censored at the date of previous tumour assessment with CR, PR, or SD.
- If the patient does not have post baseline tumour assessment nor death within 53 days for the BID or QD 5/2 schedule or 35 days for the 5/9 schedule after randomisation/enrolment, the PFS will be censored at Day 1.

PFS (in days) is calculated as:

(Date of death of documented Progression or Censoring) – (Date of randomization) +1

To apply the cut-off date to PFS is to exclude those Tumour assessments after cut-off date and anti-cancer therapy date after cut-off date in the analysis.

Progression-free survival will be derived based on scan/assessment dates not visit dates. If RECIST assessments/scans contributing towards a particular visit are performed on different dates then the date of progression will be determined based on the earliest of the dates of the component that triggered the progression. With regard to censoring, a patient will be censored at the latest of the dates contributing to a particular overall visit assessment.

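### The PFS censoring limits of 53 and 35 days are labelled 2.5 tumour assessment intervals but equal 2.5 treatment cycles, so progressions found at on-schedule scans are censored

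*Protocol*

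**What the plan says.** Section 8.4.6 of the protocol gives three censoring rules for PFS; two of them carry a time limit.

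- **Late-event rule (second bullet).** It applies when progression or death occurs "more than 53 days for the BID or QD 5/2 schedule or 35 days for the 5/9 schedule (2.5 tumour assessment intervals") after the previous assessment with CR, PR or SD. In that case "the PFS will be censored at the date of previous tumour assessment with CR, PR, or SD".
- **Day 1 rule (third bullet).** It opens: "If the patient does not have post baseline tumour assessment nor death within 53 days for the BID or QD 5/2 schedule or 35 days" (the 35 days again being for the 5/9 schedule). Such a patient is censored at Day 1.

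The scan schedule is set elsewhere. Section 8.4.5 says that "assessments are performed every 8 weeks on the BID and QD 5/9 Schedule or 9 weeks on either of the 5/2 Schedules". Section 5.1.1 ("Tumour imaging studies will be repeated every 8 weeks" for QD 5/9, then 9 weeks for QD 5/2), the study-plan tables and Appendix E agree, with a window of one week either way. Patients who stop treatment without progression "should have CT scans performed every 3 months" (footnotes to Tables 2, 3 and 4). Section 4.3.2.1 describes those scans as being for PFS.

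**The concern.** A limit expressed in scan intervals normally protects against dating an event to a scan that follows a long gap in assessment. For that it must be longer than the planned gap between scans. Limits of 35 and 53 days are shorter than 8 or 9 weeks, so the rule catches patients who attended every scan on time. The event that triggers the censoring is then the progression itself, which makes the censoring informative. Because the limits sit differently against each schedule, the 5/9, 5/2 and BID cohorts would lose events at different rates, and their PFS summaries would not be comparable.

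**Working it through.** **Inputs.** Scan interval: 56 days (BID, QD 5/9) and 63 days (both 5/2 schedules), from 8.4.5, 5.1.1 and Tables 2 to 4. Window: 7 days either way (5.1.1, Appendix E; Table 2 for BID). Cycle length: 14 days (BID, QD 5/9) and 21 days (5/2), from section 1.5. Limits: 53 days (BID, QD 5/2) and 35 days (5/9), from 8.4.6.

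**1. Trying to reproduce the limits.**

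| Schedule | Printed limit | 2.5 x scan interval | 2.5 x cycle | Limit / one scan interval |
|---|---|---|---|---|
| QD 5/9 | 35 | 2.5 x 56 = 140 | 2.5 x 14 = 35 | 35/56 = 0.63 |
| QD 5/2 (both) | 53 | 2.5 x 63 = 157.5 | 2.5 x 21 = 52.5 | 53/63 = 0.84 |
| BID | 53 | 2.5 x 56 = 140 | 2.5 x 14 = 35 | 53/56 = 0.95 |

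The stated basis does not give the printed limits. One interval (56, 63) or two (112, 126) do not give them either. Cycles give 35 exactly and 53 after rounding, except for BID, where 53 matches neither basis.

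**2. Late-event rule, next on-treatment scan.** With scans shifted a and b days from nominal (each from -7 to +7, so 15 x 15 = 225 combinations), the gap is interval + b - a.

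- QD 5/9: gaps of 42 to 70 days, all above 35. Progression at the next on-schedule scan after CR, PR or SD is always censored.
- QD 5/2: gaps of 49 to 77 days. A gap of 53 or less needs b - a of -10 or lower: 1+2+3+4+5 = 15 combinations. The other 210 of 225 (93%) are censored.
- BID: gaps of 42 to 70 days. A gap of 53 or less needs b - a of -3 or lower: 1+2+...+12 = 78 combinations. The other 147 of 225 (65%) are censored, including nominal timing (56 > 53).

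These shares weight every day of the window equally. They describe the rule and do not forecast the proportion of patients affected.

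**3. Late-event rule, off-treatment scans.** Three months is about 13 x 7 = 91 days, above both 35 and 53. Progression found at a scan 91 days after the last CR, PR or SD is censored. It would not be under 140 or 158.

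**4. Late-event rule, deaths.** A death counts only if it falls within the limit after the last qualifying scan: the first 35 of 56 days (63%) on QD 5/9, 53 of 63 (84%) on QD 5/2, and 53 of 56 (95%) on BID. Later deaths are censored.

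**5. Day 1 rule.** First on-schedule scan: QD 5/9 at 56 +/- 7 = days 49 to 63, always after 35; QD 5/2 at 63 +/- 7 = days 56 to 70, always after 53. For BID, Table 2 places it in the 7 days before Cycle 5, about days 49 to 56, so days 49 to 53 are in time and days 54 to 56 are not. The sentence has two readings:

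- The limit governs both the scan and the death. Every on-schedule QD patient alive at the limit with no earlier unscheduled scan is censored at Day 1.
- The limit governs only the death. A patient who has been scanned is not censored at Day 1.

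**The case against.** The arithmetic is hard to dispute, so the other side is about reach.

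- **Day 1 censoring.** A reader might infer that on-schedule QD patients are certainly censored at Day 1. The wording of the third bullet does not settle this, so the consequence is conditional. The late-event consequence does not depend on it.
- **All later progressions.** A reader might infer that every progression after the first scan is lost. That is exact only for QD 5/9; some gaps escape on QD 5/2 and about a third of combinations do on BID. Progression at the first scan is untouched by the second bullet, because there is no earlier post-baseline CR, PR or SD.
- **Deaths.** A reader might infer that most deaths are censored. Under the second bullet the reverse holds: more than half of each between-scan interval lies within the limit. Heavy loss of deaths could arise only through the stricter reading of the third bullet.
- **PFS made worthless.** The documents do not support so strong a claim. If the Day 1 rule spares scanned patients, first-scan progressions and many deaths remain as events, and the summary is distorted but not empty. Its numerical bias would depend on event rates that the protocol does not give.
- **Importance.** PFS is not among the primary, secondary or exploratory outcome measures in section 2, section 8.4 plans no formal testing, and cohorts have 3 to 6 patients, or up to 12 if expanded. Scan dates are collected, so a corrected derivation loses nothing.

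All five points stand. They limit the consequence but do not remove the contradiction between the limits and their stated basis.

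**Conclusion.** The rule is wrong as written. The limits of 53 and 35 days are not 2.5 tumour assessment intervals; those are 140 and 157.5 days. The printed values match treatment cycles, and BID matches neither. Under the second bullet, progression at the next on-schedule scan is censored in all QD 5/9 cases, in 93% of window combinations on QD 5/2, and at nominal timing (65% of combinations) on BID. Progression at 3-monthly off-treatment scans and deaths beyond the limit are also censored. Day 1 censoring of on-schedule QD patients follows only if the limit in the third bullet governs the assessment as well as the death.

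This rests on the scan intervals and windows in the protocol and on taking the parenthetical basis in 8.4.6 as the intent. Severity is moderate: a descriptive PFS summary is biased and not comparable across schedules, while the MTD, DLT, safety, PK and response objectives are unaffected.

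**What to change.** In section 8.4.6:

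1. In both bullets, replace the limits by 140 days for BID and QD 5/9 and 158 days for both QD 5/2 schedules (2.5 x 56 = 140; 2.5 x 63 = 157.5, rounded up), in line with the stated basis. This also moves BID into the group that shares its scan interval.
2. Reword the third bullet so that it has one meaning, for example: a patient with no post-baseline tumour assessment at all, who also did not die within 140 days (BID, QD 5/9) or 158 days (QD 5/2 schedules) of the first dose, is censored at Day 1. With the corrected limits an on-schedule patient is safe on either reading, since the first scan is due by day 63 or 70, but the text should still choose.
3. Carry the same limits and wording into the SAP and the programming.

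One detail is worth settling at the same time. The first off-treatment scan is timed from the last dose, so if the last on-treatment scan was nearly a full interval earlier, the gap on an 8-week schedule could reach about 56 + 91 = 147 days, just over 140. A sentence on how the limit applies after treatment stops would cover it.

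The cost is an edit to two bullets and the matching derivation. No patient, visit, scan or data item changes.

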8.4.7 Changes in target lesions

Waterfall plots indicating the best percentage change from baseline in the sum of longest diameters of TL will be produced for the dose level cohorts.

Spider Plots charting change in tumour size across visits will be produced. It will include all visits, including unscheduled.

8.4.8 Pharmacokinetics

Pharmacokinetics will be summarised as per the PK analysis set.

All plasma concentration data for AZD1775 and derived PK parameters will be summarised and presented according to AstraZeneca standards as described in the SAP.

8.4.9 Timing of analyses

A formal review of safety and PK data by the SRT will occur at the end of each dose escalation cohort prior to opening the next dose level cohort.

The final analysis will take place when patients completed protocol specified follow-up or at an earlier time if deemed appropriate by the SRT and/or AstraZeneca.

8.5 Evaluation and calculation of variables by AstraZeneca or delegate

8.5.1 Calculation or derivation of pharmacokinetic variables

Pharmacokinetic analysis: For AZD1775 concentration data will be performed by Covance on behalf of AstraZeneca. The actual sampling times will be used in the parameter calculations and PK parameters will be derived using standard non-compartmental methods.

When possible the following PK parameters will be determined:

- C_{\max}
- $C_{8\text{hr}}$ or $C_{10\text{hr}}$
- Time to C_{\max} (t_{\max})
- Time of last detectable concentration (t_{last})
- Terminal half-life ($t_{1/2\lambda z}$)

- Area under the plasma concentration-time curve from zero to 10 hours ($AUC_{(0-10)}$) from zero to the time of the last measurable concentration ($AUC_{(0-t)}$), and from zero to 24 hours ($AUC_{(0-24)}$).
- C_{trough}

The C_{max} and t_{max} parameters will be determined by inspection of the concentration time profiles. Where possible the terminal elimination rate constant (λ_z) will be calculated by log linear regression of the terminal portion of the concentration-time profiles when there are sufficient data and the terminal elimination half-life ($t_{1/2\lambda_z}$) will be calculated as $\ln 2/\lambda_z$. The area under the concentration-time curve up to the last quantifiable sample ($AUC_{[0-t]}$) and the $AUC_{(0-10)}$ will be calculated using the linear up, log down trapezoidal rule. Where appropriate, the $AUC_{(0-t)}$ will be extrapolated to infinity using λ_z to obtain AUC. The apparent oral steady state clearance CL_{ss}/F following multiple dosing will be determined from the ratio of dose/ $AUC_{(0-24)}$. The apparent volume of distribution (V_z/F) will be determined from the CL/F divided by λ_z , as appropriate.

Assessment of food effect: For AZD1775 natural log-transformed AUC and C_{max} will be compared between treatments using a mixed effects analysis of variance model. Estimates of the mean difference between treatments and corresponding 90% confidence intervals (CI) will be calculated. The mean differences and the CIs will be back transformed to the original scale in order to give estimates of the geometric mean ratio and the associated 90% CIs. Additionally, back transformed geometric means together with 95% CIs will be estimated and presented for each food condition. Additional AUCs will be analysed if appropriate.

8.6 Pharmacokinetics/Pharmacodynamic Analysis

The plasma concentration data for AZD1775 may be analysed using a population PK approach, which may include exploring the influence of covariates on PK, if the data allows. A population PDx approach will be used to investigate the relationship between PK and selected primary, secondary and/or exploratory endpoints, where deemed appropriate. Results may be reported separately from the CSR for the main study.

The PK, PDx, demographic, safety and tumour response data collected in this study may also be combined with similar data from other studies and explored using population PK and/or PK-PDx methods. The results of any such analyses will be reported separately from the CSR.

9. STUDY AND DATA MANAGEMENT BY ASTRAZENECA

9.1 Training of study site personnel

Before the first patient is entered into the study, an AstraZeneca designee will review and discuss the requirements of the CSP and related documents with the investigational staff and also train them in any study specific procedures and the EDC system(s) utilised.

The PI will ensure that appropriate training relevant to the study is given to all of these staff, and that any new information relevant to the performance of this study is forwarded to the staff involved.

The PI will maintain a record of all individuals involved in the study (medical, nursing and other staff).

9.2 Monitoring of the study

During the study, an AstraZeneca designee will have regular contacts with the study site, including visits to:

- Provide information and support to the Investigator(s)
- Confirm that facilities remain acceptable
- Confirm that the investigational team is adhering to the protocol, that data are being accurately and timely recorded in the eCRFs, that biological samples are handled in accordance with the Laboratory Manual and that study drug accountability checks are being performed
- Perform source data verification (SDV [a comparison of the data in the CRFs with the patient's medical records at the hospital or practice, and other records relevant to the study]) including verification of informed consent of participating patients. This will require direct access to all original records for each patient (e.g., clinic charts)
- Ensure withdrawal of informed consent to the use of the patient's biological samples is reported and biological samples are identified and disposed of/destroyed accordingly, and the action is documented and reported to the patient.

The AstraZeneca designee will be available between visits if the Investigator(s) or other staff at the centre need information and advice about the study conduct.

9.2.1 Source data

Refer to the CSA for location of source data.

9.2.2 Study agreements

The PI at each centre should comply with all the terms, conditions, and obligations of the CSA, or equivalent, for this study. In the event of any inconsistency between this CSP and the CSA, the terms of the CSP shall prevail with respect to the conduct of the study and the treatment of patients, and in all other respects, not relating to study conduct or treatment of patients, the terms of the CSA shall prevail.

Agreements between AstraZeneca or its designee and the PI should be in place before any study-related procedures can take place or patients are enrolled.

9.2.3 Archiving of study documents

The Investigator follows the principles outlined in the CSA.

9.3 Study timetable and end of study

The end of the study is defined as ‘the last visit of the last subject undergoing the study’.

There will be a data cut-off for preparation of a CSR. Any patients still receiving AZD1775 at the time of the primary data cut-off will complete a FPV, which should align with the next scheduled visit following implementation of the CSP Version 5. Refer to Section 4.3.2.3 for further information regarding the FPV.

Patients continuing beyond FPV (Section 4.3.2.3) will continue to be monitored for all SAEs, pregnancies, and overdoses for 30 days after the last dose of the investigational product. Investigators must report SAEs, overdoses, and pregnancies to the AstraZeneca representative in accordance with Sections 6.4, 6.5, and 6.6, and continue to maintain study drug accountability as long as patients are receiving treatment with the study drug. The study is expected to start in Q4 2015 and end by the last visit of the last patient undergoing the study.

The study may be terminated at individual centres if the study procedures are not being performed according to Good Clinical Practice (GCP), or if recruitment is slow. AstraZeneca may also terminate the entire study prematurely if concerns for safety arise within this study or in any other study with AZD1775.

